5.4.3.2 Pregnancies in Female Partners of Male Patients

Male patients will be instructed through the Informed Consent Form to immediately inform the investigator if their partner becomes pregnant during the study or within 3 months after the last dose of study treatment. A Clinical Trial Pregnancy Reporting Form should be completed and submitted to the Sponsor or its designee immediately (i.e., no more than 24 hours after learning of the pregnancy), either by faxing or by scanning and emailing the form using the fax number or email address provided to investigators. Attempts should be made to collect and report details of the course and outcome of any pregnancy in the partner of a male patient exposed to study treatment. *When permitted by the site, the pregnant partner would need to sign an Authorization for Use and Disclosure of Pregnancy Health Information to allow for follow-up on her pregnancy. If the authorization has been signed, the investigator should submit a Clinical Trial Pregnancy Reporting Form when updated information on the course and outcome of the pregnancy becomes available.* An investigator who is contacted by the male patient or his pregnant partner may provide information on the risks of the pregnancy and the possible effects on the fetus, to support an informed decision in cooperation with the treating physician and/or obstetrician.

5.4.3.3 Exposure of Pregnant Female to Lenalidomide

If a pregnant female not enrolled in the study (e.g., caregiver or pharmacist) is exposed to lenalidomide, the Adverse Event Form provided to investigators should be completed and submitted to the Sponsor or its designee immediately (i.e., no more than 24 hours

after learning of the exposure), either by faxing or by scanning and emailing the form using the fax number or email address provided to investigators. The woman should be referred to an obstetrician or gynecologist, preferably one who is experienced in reproductive toxicity, for further evaluation and counseling.

5.4.3.4 Abortions

A spontaneous abortion should be classified as a serious adverse event (as the Sponsor considers abortions to be medically significant), recorded on the Adverse Event eCRF, and reported to the Sponsor immediately (i.e., no more than 24 hours after learning of the event; see Section 5.4.2).

If a therapeutic or elective abortion was performed because of an underlying maternal or embryofetal toxicity, the toxicity should be classified as a serious adverse event, recorded on the Adverse Event eCRF, and reported to the Sponsor immediately (i.e., no more than 24 hours after learning of the event; see Section 5.4.2). A therapeutic or elective abortion performed for reasons other than an underlying maternal or embryofetal toxicity is not considered an adverse event.

All abortions should be reported as pregnancy outcomes on the paper Clinical Trial Pregnancy Reporting Form.

5.4.3.5 Congenital Anomalies/Birth Defects

Any congenital anomaly/birth defect in a child born to a female patient exposed to study treatment or the female partner of a male patient exposed to study treatment should be classified as a serious adverse event, recorded on the Adverse Event eCRF, and reported to the Sponsor immediately (i.e., no more than 24 hours after learning of the event; see Section 5.4.2).

5.5 FOLLOW-UP OF PATIENTS AFTER ADVERSE EVENTS

5.5.1 Investigator Follow-Up

The investigator should follow each adverse event until the event has resolved to baseline grade or better, the event is assessed as stable by the investigator, the patient is lost to follow-up, or the patient withdraws consent. Every effort should be made to follow all serious adverse events considered to be related to study treatment or trial-related procedures until a final outcome can be reported.

During the study period, resolution of adverse events (with dates) should be documented on the Adverse Event eCRF and in the patient's medical record to facilitate source data verification.

All pregnancies reported during the study should be followed until pregnancy outcome.

5.5.2 Sponsor Follow-Up

For serious adverse events, adverse events of special interest, and pregnancies, the Sponsor or a designee may follow up by telephone, fax, electronic mail, and/or a monitoring visit to obtain additional case details and outcome information (e.g., from hospital discharge summaries, consultant reports, autopsy reports) in order to perform an independent medical assessment of the reported case.

5.6 ADVERSE EVENTS THAT OCCUR AFTER THE ADVERSE EVENT REPORTING PERIOD

After the end of the adverse event reporting period (defined as 35 days after the last dose of study treatment), all deaths, regardless of cause, should be reported through use of the Long-Term Survival Follow-Up eCRF.

In addition, if the investigator becomes aware of a serious adverse event that is believed to be related to prior exposure to study drug, the event should be reported through use of the Adverse Event eCRF.

An exception is made for Grade 3–4 infections (related and unrelated to study treatment), which should be reported until up to 2 years after the last dose of study treatment. In addition, SPMs (related and unrelated to study treatment) should be reported as serious adverse events until up to 3 years after the last dose of lenalidomide.

The Sponsor should also be notified of events of second malignancies indefinitely (even if the G+Atezo+len treatment group or the overall study has been closed) for patients who received obinutuzumab.

If the EDC system is not available, the investigator should report these events directly to the Sponsor or its designee, either by faxing or by scanning and emailing the paper Clinical Trial Serious Adverse Event/Adverse Event of Special Interest Reporting Form using the fax number or email address provided to investigators.

5.7 EXPEDITED REPORTING TO HEALTH AUTHORITIES, INVESTIGATORS, INSTITUTIONAL REVIEW BOARDS, AND ETHICS COMMITTEES

The Sponsor will promptly evaluate all serious adverse events and adverse events of special interest against cumulative product experience to identify and expeditiously communicate possible new safety findings to investigators, IRBs, ECs, and applicable health authorities based on applicable legislation.

To determine reporting requirements for single adverse event cases, the Sponsor will assess the expectedness of these events using the following reference document:

- Obinutuzumab Investigator's Brochure
- Atezolizumab Investigator's Brochure
- Lenalidomide Summary of Product Characteristics

The Sponsor will compare the severity of each event and the cumulative event frequency reported for the study with the severity and frequency reported in the applicable reference document.

Reporting requirements will also be based on the investigator's assessment of causality and seriousness, with allowance for upgrading by the Sponsor as needed.

6. STATISTICAL CONSIDERATIONS AND ANALYSIS PLAN

The study will include an initial dose-escalation phase followed by an expansion phase. The dose-escalation phase is designed to determine the RP2D for lenalidomide when combined with fixed doses of obinutuzumab and atezolizumab. During the expansion phase, patients will undergo treatment with lenalidomide at the RP2D, obinutuzumab, and atezolizumab.

6.1 DETERMINATION OF SAMPLE SIZE

Limited dose finding will be conducted during the dose-escalation phase of this study. The estimated sample size follows from the dose-escalation rules for a 3+3 algorithm, as outlined in Section 3.1. It is anticipated that enrollment of two dosing groups of 3–6 patients each, for a total of 6–12 patients with relapsed or refractory FL, will be required to establish the RP2D during the dose-escalation phase.

Approximately 40 patients will be enrolled during the expansion phase.

The primary efficacy analysis will be the estimation of the true proportion of patients expected to obtain a PET-CT–defined CR at EOI.

Data from completed and ongoing studies in similar disease settings will be used as historical controls for comparison. Currently available data from the GALEN study (Morschhauser et al. 2017) indicate that the historical CR rate based on PET-CT scans is approximately 40% in relapsed or refractory setting, as assessed by Cheson 2007 criteria.

A sample size of 40 patients is deemed sufficient to provide adequate precision for the point estimate and for the lower bound of the two-sided 90% CI to rule out a clinically uninteresting probability of response of < 46%, assuming an observed PET-CT–defined CR rate of 60%. Updated estimates of the proportion of patients expected to achieve a

PET-CT–defined CR are expected to be available from ongoing studies by the time of the first interim analysis and will be used as reference data.

Table 14 lists the two-sided 90% Clopper-Pearson exact CI for the true probability of achieving a PET-CT–defined CR at the EOI for a range of observed proportions based on a sample of 40 patients.

Table 14 Potential 90% CI for the True Probability of Achieving a PET-CT–Defined Complete Response at EOI

Observed Proportion of Patients Achieving a PET-CT–Defined CR at EOI (n=40)	Two-Sided 90% Clopper-Pearson CI ^a for True Population PET-CT–Defined CR (n=40)
0.32	(0.20, 0.46)
0.50	(0.36, 0.64)
0.55	(0.40, 0.68)
0.60	(0.46, 0.73)
0.65	(0.51, 0.77)
0.70	(0.56, 0.82)
0.72	(0.58, 0.83)
0.75	(0.61, 0.86)
0.80	(0.66, 0.89)
0.85	(0.72, 0.93)

CI= confidence interval; CR= complete response; CT= computed tomography; EOI= end of induction; PET= positron emission tomography.

^a Note that the lower limit of a two-sided 90% CI is equivalent to a one-sided 95% CI.

6.2 DEFINITION OF ANALYSIS POPULATIONS

The following populations are defined:

- The primary population will include patients who received at least one dose of each component of the combination.
- The intent-to-treat (ITT) population will include all patients enrolled in the study.

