For the Q4W dosing interval, the fixed dose of 1680 mg Q4W is the equivalent of a weight-based dose of 15 mg/kg Q3W. Population PK modeling suggests that the area under the concentration-time curve (AUC) would be comparable to that of 1200 mg Q3W (data available on request). The current manufacturing process considers 1200 mg the maximum daily dose for clearance of manufacturing process-derived impurities (such as host-cell DNA and endotoxins) to safe levels. The manufacturing processes for atezolizumab are capable of clearing such impurities to safe levels, and tests for impurities are performed as a part of the manufacturing processes. However, the total dose of 1680 mg will be split into two daily doses to minimize the theoretical risk of exceeding safe limits.

In Study PCD4989g, atezolizumab was safely administered to 11 patients with various hematologic malignancies (including 7 patients with lymphoma) at doses of 15 mg/kg Q3W (n= 1) or 20 mg/kg Q3W (n= 10). Atezolizumab 1200 mg Q3W is currently being evaluated in combination with obinutuzumab in an ongoing Phase Ib study (GO29383) in patients with relapsed or refractory DLBCL or FL (see Section 1.4.3.2). Atezolizumab is

added to obinutuzumab starting with Cycle 2 to avoid overlapping IRRs during the first infusion of obinutuzumab, which is known to be associated with the highest incidence and risk of severe IRRs. The combination has been safely administered in the first 6 patients who were evaluable for DLTs. Consistent with the dosing schedule used in Study GO29383, in this study, atezolizumab will be added to G-Len starting with Cycle 2.

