4.3.2.4 Induction Treatment with Atezolizumab, Obinutuzumab, and Lenalidomide (Atezo+G+Len)

Patients will receive induction treatment, administered in 28-day cycles as follows:

- Patients will receive six cycles of induction treatment consisting of obinutuzumab and lenalidomide for Cycles 1–6 and atezolizumab for Cycles 2–6 as outlined in [Table 4](#).

Lenalidomide may be administered before or concomitantly with obinutuzumab. After completion of the obinutuzumab infusion, the line will be flushed (unless there is a central line with more than one line/port), after which atezolizumab will be administered.

For patients at increased risk for IRRs (high tumor burden), the obinutuzumab infusion may be split and administered over 2 days, with 100 mg given on Day 1 and 900 mg given on Day 2.

For patients who experience an IRR during obinutuzumab infusion, administration of atezolizumab may be delayed by 1 day if clinically required.

Table 4 Induction Treatment

Treatment	Dose	Route	Regimen (28-Day Cycles)	
			Cycle 1	Cycles 2–6
Lenalidomide	Dose-escalation phase: 15 or 20 mg ^a Expansion phase: RP2D	PO	Days 1–21	Days 1–21
Obinutuzumab	1000 mg	IV	Days 1, 8, and 15	Day 1
Atezolizumab	840 mg	IV	—	Days 1 and 15

IV=intravenous; PO=by mouth; RP2D=recommended Phase II dose.

^a Dose may be de-escalated to 10 mg.

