5.3.1 Adverse Event Reporting Period

Investigators will seek information on adverse events at each patient contact. All adverse events, whether reported by the patient or noted by study personnel, will be recorded in the patient's medical record and on the Adverse Event eCRF.

After informed consent has been obtained **but prior to initiation of study treatment**, only serious adverse events caused by a protocol-mandated intervention (e.g., invasive procedures such as biopsies, discontinuation of medications) should be reported (see Section 5.4.2 for instructions for reporting serious adverse events).

After initiation of study treatment, all adverse events will be reported until 35 days after the last dose of study treatment. After this period, the investigator should report any serious adverse events that are believed to be related to prior study treatment (see Section 5.6).

An exception is made for Grade 3–4 infections (related and unrelated to study treatment), which should be reported until up to 2 years after the last dose of study treatment; and for SPMs (related and unrelated), which should be reported as serious adverse events until up to 3 years after the last dose of lenalidomide.

Similarly, second malignancies (related and unrelated to study treatment) will be reported indefinitely (even if the study has been closed) for patients who received obinutuzumab (see Section 5.6).

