6.5 SAFETY ANALYSES

The safety analysis will be performed on the primary population; additional safety analysis will be performed on the ITT population.

The safety analyses will be performed separately for each study phase (i.e., dose escalation and expansion).

Safety will be assessed through summaries of adverse events, changes from baseline in laboratory test results, laboratory data with values outside of the normal ranges, ECGs, and vital signs.

All adverse events occurring on or after the first study treatment will be summarized by mapped term, appropriate thesaurus levels, and NCI CTCAE v4.0 grade. All serious adverse events, adverse events of special interest, and selected events will be summarized and listed.

Deaths reported during the treatment period and during post-treatment follow-up will be listed.

Relevant laboratory and vital sign data will be displayed by time, with Grade 3 and 4 values identified as appropriate.

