6.6 EFFICACY ANALYSES

6.6.1 Primary Efficacy Endpoint

The efficacy analysis will be performed on the primary population. Additional efficacy analysis will be performed on the ITT population.

Patients who received lenalidomide at the RP2D during the dose-escalation phase will be pooled with patients treated in the expansion phase.

The primary efficacy analysis will be estimation of the proportion of patients achieving a CR at EOI, as determined by the IRC through use of the PET-CT–based Lugano 2014 criteria (see [Appendix 3](#)). Point estimates will be presented, along with the corresponding two-sided 90% Clopper-Pearson exact CIs. Patients without an EOI tumor assessment will be considered non-responders.

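### The main safety tables leave out patients who received study drug but never atezolizumab, because the primary population requires a dose of all three drugs and no any-dose safety set is defined

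*Combined protocol and SAP*

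**What the plan says.** Section 6.2 defines two analysis sets. The first: "The primary population will include patients who received at least one dose of each component of the combination". The second is ITT, which is everyone enrolled.

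Section 6.5 assigns the main safety work to the first set: "The safety analysis will be performed on the primary population". ITT safety is additional, and results are reported separately for dose escalation and expansion. The same section says: "All adverse events occurring on or after the first study treatment will be summarized". Section 5.3.1 collects events on the same footing: "After initiation of study treatment, all adverse events will be reported until 35 days after the last dose of study treatment".

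Section 4.3.2.4 gives the induction schedule: "obinutuzumab and lenalidomide for Cycles 1–6 and atezolizumab for Cycles 2–6". Section 3.3.2.1 explains that atezolizumab is held back to avoid overlapping infusion-related reactions (IRRs) with the "first infusion of obinutuzumab, which is known to be associated with the highest incidence and risk of severe IRRs".

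For efficacy, Section 6.6.1 also uses the primary population first and ITT as additional, with the rule: "Patients without an EOI tumor assessment will be considered non-responders". Under Section 4.6.2, an expansion patient who stops before receiving all three drugs is replaced.

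**The concern.** A safety set is normally defined by exposure to any study drug, so that nobody who was at risk drops out because of what happened next. Here a patient must survive Cycle 1 and remain on treatment long enough to receive a drug that starts in Cycle 2. Section 4.6.2 permanently stops study treatment for anaphylaxis, acute respiratory distress, a Grade 4 IRR or a life-threatening event, and Table 11 repeats the rule for anaphylaxis. Some of the most serious Cycle 1 reactions can therefore remove the patient from the main safety tables. This falls in the period that the protocol itself links to the highest risk of severe IRRs.

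It also conflicts with the Section 6.5 commitment on adverse events from first treatment: the events are collected, but the main tables omit some of the patients who had them. At stake is whether the headline safety results describe everyone exposed.

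**Working it through.** **Who is excluded.**
1. Entry to the primary population needs at least one dose of lenalidomide, of obinutuzumab and of atezolizumab (Section 6.2).
2. Cycle 1 contains only lenalidomide and obinutuzumab (Section 4.3.2.4, Table 4).
3. A patient who receives either Cycle 1 drug but never atezolizumab is therefore outside the set. Routes include death, withdrawal of consent, and permanent discontinuation for toxicity.
4. Cycle 1 events in patients who do go on to atezolizumab (having received all three drugs) are kept. A patient who stops only one of the Cycle 1 drugs after receiving it may continue the other two (Section 4.6.2) and can still qualify.
5. ITT contains these patients, but it also contains anyone enrolled and never dosed. Neither set equals all treated patients.

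**Method.** Two-sided 90% Clopper-Pearson limits, as in Section 6.6.1: lower = Beta quantile at 0.05 with parameters (x, n − x + 1); upper = Beta quantile at 0.95 with parameters (x + 1, n − x). The plan names no interval for safety, so the same method is used there for illustration only.

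**Reproducing the plan.** Table 14 prints (0.46, 0.73) for an observed 0.60 with n = 40. For 24/40 the limits are 0.4578 and 0.7306, which agree.

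**Safety illustration.** The number of excluded patients is an assumption (1 or 2). Because expansion patients are replaced, the primary set stays at 40 and the excluded patients are extra.

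| Case | Main table as planned | Any-dose set |
|---|---|---|
| Expansion, one Cycle 1 death | 0/40, upper limit 1 − 0.05^(1/40) = 7.2% | 1/41 = 2.4%, upper limit 11.1% |
| Expansion, two Cycle 1 deaths | 0/40, upper limit 7.2% | 2/42 = 4.8%, upper limit 14.2% |
| Escalation group of 6, one death | 0/6, upper limit 1 − 0.05^(1/6) = 39.3% | 1/7 = 14.3%, upper limit 52.1% |

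**Effect on the CR rate.** Appendix 1 (footnote ee) schedules end-of-induction (EOI) imaging only after at least two induction cycles. A patient treated only in Cycle 1 would have no EOI scan and would count as a non-responder, but the population definition removes that patient before the rule can apply. Adding such patients with the CR count fixed:

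| Base | None added | One added | Two added |
|---|---|---|---|
| Table 14 (n = 40) | 24/40 = 60.0%, lower limit 45.8% | 24/41 = 58.5%, 44.5% | 24/42 = 57.1%, 43.3% |
| Pooled, about 46 | 28/46 = 60.9%, lower limit 47.7% | 28/47 = 59.6%, 46.5% | 28/48 = 58.3%, 45.5% |

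Each such patient lowers the rate by 1.2 to 1.5 points. The interval for 24/40 is 73.1 − 45.8 = 27.3 points wide.

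**The opposite case.** Table 11 allows obinutuzumab and lenalidomide to be given without atezolizumab if a delay of more than 21 days is expected. After Grade 3 or 4 non-infectious pneumopathy it stops atezolizumab permanently and allows the other two to resume. A patient on that path from Cycle 1 could complete two or more cycles, have an EOI scan and be a CR: 25/41 = 61.0% against 24/40 = 60.0%. Inclusion would then raise the estimate.

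**The case against.** The strongest reply is that the plan already covers these patients. ITT safety and efficacy analyses are pre-specified. A never-dosed patient contributes no events from first treatment onward, so ITT and any-dose event counts would be the same and only the denominators could differ. The sponsor approves each enrolment and treatment should start within 28 days of consent, so few undosed patients are likely. If everyone enrolled is dosed, the ITT expansion table shows the illustrated death as 1/41. Section 6.5 also lists deaths, Section 6.3 lists discontinuations, and nothing excludes these patients from the Internal Monitoring Committee's monitoring of deaths and fatal events. This stands as far as it goes: the data are not lost. It does not answer why the main table, rather than the additional one, should omit treated patients.

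For efficacy, an exposure-based set is a defensible way to estimate the activity of the triplet in a single-arm study. It matches the replacement rule and has an ITT estimate beside it. That stands.

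A reader might infer three stronger points, none of which the documents support:
- **That the definition biases results in favour of the regimen.** The 25/41 case shows the CR rate can move either way. So can a safety rate: an event-free withdrawal in Cycle 1 only enlarges the denominator, for example from 2/40 = 5.0% to 2/41 = 4.9%.
- **That exclusion makes the difference in ruling out 46%.** The planning case is already at 45.8% before rounding, and 46% is a precision target, not a formal test.
- **That the Section 6.11 percentages should move to the any-dose set.** That section names no population, so this is a separate question. A larger denominator could also weaken a trigger: 30/40 = 75.0% meets the Grade 3–4 threshold and 30/41 = 73.2% does not.

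**Conclusion.** The point holds for safety and should be fixed. The main safety set excludes treated patients, for reasons that can include severe Cycle 1 toxicity, and no set of all treated patients exists to replace it. The size cannot be stated, because the number of patients who never reach atezolizumab is not in the documents and may be zero. Table 8 reports no Grade 3 or 4 IRRs related to study drug during induction with obinutuzumab plus lenalidomide, against 11% for obinutuzumab alone. The tabulated death rates are illustrations that assume one or two excluded patients, each with a fatal event. In a group of about 40, a single such patient is the difference between reporting no deaths and reporting one.

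For efficacy the point is minor. A patient with no EOI scan would lower the CR rate by about 1 to 1.5 points, which is small beside the interval, and the overall direction is not established.

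**What to change.** In Section 6.2 and the synopsis, add a safety population of all patients who received at least one dose of any study drug. In Section 6.5 and the matching synopsis text, make it the set for the main safety outputs, still reported by phase. State in the amendment and the study report that the set was added by amendment.

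Leave the efficacy analyses as they are: the primary-population CR estimate with the pre-specified ITT estimate. No change to the Section 6.11 denominators is part of this point.

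The cost is wording in the synopsis and two sections, and the matching table specifications. No new data are needed, since adverse events are already collected from first treatment.
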